- Where providing triamcinolone 0.1% cream and/or hydrocortisone 2.5% ointment is not possible, an equivalent-potency TCS cream and/or ointment that is in line with local practices can be supplied by the sites. Refer to [Appendix 8](#) for guidance on potency equivalence.

- Where possible, TCS use when supplied by the site should also be recorded via weight of returned tubes, as indicated in the Schedule of Activities (Section 2); however, where this is not practical, this information does not need to be recorded, and will not be considered a protocol violation.
- If the TCS supplied by the sponsor is not considered suitable for an individual patient, an equivalent-potency TCS cream and/or ointment that is in line with local practices can be supplied by the sites. Refer to [Appendix 8](#) for guidance on potency equivalence.

Choice of High- and Ultra-High-Potency Topical Corticosteroids for Rescue

The use and choice of specific high- or ultra-high-potency TCS for rescue is at the discretion of the investigator and it will not be provided by the sponsor. The weights of returned tubes of the high- and ultra-high-potency TCS are not required.

Other Topical Treatments

Investigators may also select to use TCNIs and/or crisaborole in countries where approved, in place of TCS. If TCNIs or crisaborole are prescribed, use should be limited to problem areas (e.g., face, neck, skin folds, genital areas, etc.).

Use of all topical treatments for AD must be recorded in the CRF.

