7.7.4. Rescue Therapy

For patients who are experiencing worsening and unacceptable symptoms of AD despite treatment with investigational product and moderate-potency TCS, rescue therapy with additional topical and systemic therapies is available starting after 2 weeks of treatment (Visit 4). Use of rescue medications should be limited to patients where control of symptoms cannot be achieved with increased emollient use and background TCS (low potency and moderate potency). Prior to rescue, control of AD symptoms should be attempted by avoiding exacerbating factors, intensifying emollient applications, and using only the permitted study treatments, including background TCS therapy (e.g., triamcinolone 0.1% cream and/or hydrocortisone 2.5% ointment) (Section 7.7.2).

Rescue with High- and Ultra-High-Potency TCS

Patients whose lesions persist or worsen despite the use of emollients and background TCS therapy (e.g., triamcinolone 0.1% cream and/or hydrocortisone 2.5% ointment) and/or patients who require prolonged applications of triamcinolone 0.1% cream (moderate-potency TCS) on large surfaces may be considered for rescue to high- or ultra-high-potency TCS ([Appendix 8](#) for TCS potency).

High- or ultra-high-potency TCS may be used once daily for up to 14 consecutive days or less, or based on the maximum duration recommended in the prescribing information.

It is recommended that if a patient reaches “clear” to “almost clear” skin after topical rescue, then moderate-, high-, or ultra-high-potency TCS should be stopped, and low-potency TCS (e.g., hydrocortisone 2.5% ointment) should be used once daily for an additional 7 days, then stopped.

Patients rescued with high- or ultra-high-potency TCS will continue to take investigational product and use of topical rescue therapy will be documented in the eCRF.

Rescue with Systemic Therapies

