If topical rescue therapy as described above fails to sufficiently control AD symptoms, then oral systemic medications may be used as rescue (e.g., corticosteroids, cyclosporine, and methotrexate); however, investigational product will be required to be permanently discontinued for the remainder of the 16-week study duration. If these medications are needed for other medical conditions (e.g., asthma flare), they will still be treated as rescue medications. These patients are still eligible to enter the long-term extension study (JAHN), if they complete the schedule of study visits through Visit 8 (Week 16) and are also able to complete a minimum 4-week washout from oral systemic rescue medications (which can occur during the screening period for Study JAHN).

Investigators should make every attempt to conduct efficacy and safety assessments immediately before administering any rescue treatment. An unscheduled visit can be used for this purpose if necessary.

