### 6.4. Handling of Dropouts or Missing Data

Intercurrent events (ICH E9 R1) are events which occur after the treatment initiation and make it impossible to measure a variable or influence how it would be interpreted.

Depending on the estimand being addressed, different methods will be used to handle missing data as a result of intercurrent events. Intercurrent events can occur through the following:

- application of one of the censoring rules (including after permanent study drug discontinuation or after rescue therapy)
- discontinuation

- missing an intermediate visit prior to discontinuation or rescue
- lost to follow-up.

Non-censor intercurrent events are events that are not due to the application of any censoring rule, i.e., the last 3 items in the list above.

Note that as efficacy and health outcome data can accrue after a patient permanently discontinues study drug or begins rescue therapy, specific general censoring rules to the data will be applied to all efficacy and health outcome observations subsequent to these events depending on the estimand being addressed. These specific censoring rules are described below.

The *primary censoring rule* will censor efficacy and health outcome data after permanent study drug discontinuation or after rescue therapy. This censoring rule will be applied to all continuous and categorical efficacy and health outcome endpoints. This censoring rule is equivalent to using all the data up to rescue.

A *secondary censoring rule* will only censor efficacy and health outcome data after permanent study drug discontinuation. This sensitivity analysis will include all observed values up to study drug discontinuation. The secondary censoring rule will be applied to primary and key secondary efficacy and health outcome endpoints as sensitivity analyses.

Table JAIY.6.1 describes the planned imputation methods for efficacy and health outcome endpoints with associated censoring rules. Sections 6.4.1 through 6.4.5 summarize the methodology of each imputation rule.

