For moderate potency TCS, the dispensed tube weight with cap (without the carton) in Japan is 13.5g. For countries supplied by European distributors, the dispensed weight of moderate potency TCS is 38g. The remaining countries, supplied by US distributors, the weight of moderate potency TCS is 40g. The total amount of background TCS, provided by sponsor, will be summarized in grams by potency (low and moderate) and both potencies, between visits (Week 0 through Week 1, Week 1 through Week 2, Week 2 through Week 4, Week 4 through Week 8, Week 8 through Week 12, Week 12 through Week 16), and throughout the entire 16-week treatment period. If a returned tube is not weighed or not returned, then the tube can be classified as partially used, fully used, unused, or unknown. Partially used rescue medication tubes will be defined as 50% used whereas fully used and unused tubes will be defined as 100% and 0% used respectively. When drug accountability is not performed for a particular tube of rescue medication or an answer of 'unknown' is given for a tube which is not returned, that particular tube will not be included in the analysis. The main analysis on the total amount of background TCS throughout the entire 16-week treatment period will apply censoring rule #1. After patients who get rescued or discontinue IP, whichever is earlier, it is assumed that they would use the same amount of TCS as they did before. Analysis will be done via analysis of variance (ANOVA), with geographic region, baseline disease severity and treatment as factors in the model. The secondary analysis will apply censoring rule #2 with the same assumptions as described above.

Whether any background TCS is used or not used for each patient is also collected on the diary device in each day starting from the first dose date throughout the study.

The total number of days that the patients did not use background TCS will be summarized by both potencies throughout the entire 16-week treatment period. The main analysis applies censoring rule #1. After patients who are rescued or discontinue IP, it is assumed that background TCS would be applied each day. In case of missing values in the daily diary, it will be assumed that background TCS has been used. Analysis will be done via ANOVA, with geographic region, baseline disease severity and treatment as factors in the model. A secondary analysis will apply censoring rule #2, with the same assumptions for missing values as described above.

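### In the secondary (rule #2) analysis of days without background TCS, a day on high-potency rescue TCS can count as TCS-free, which can bias the comparison if topical rescue differs between arms

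*SAP*

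**What the plan says.** SAP 4.2.2 lists two background-TCS endpoints over 16 weeks, mean grams used and mean days without use. Both are other secondary endpoints without multiplicity adjustment. SAP 6.11.1 analyses each one twice, under censoring rules #1 and #2. SAP 6.4 does not use those labels. It defines a primary rule, which "will censor efficacy and health outcome data after permanent study drug discontinuation or after rescue therapy", and a secondary rule, which "will only censor efficacy and health outcome data after permanent study drug discontinuation". I read #1 and #2 as these two.

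- **Grams (SAP 6.11.1).** "The total amount of background TCS, provided by sponsor, will be summarized in grams by potency (low and moderate) and both potencies". After rescue or stopping study drug, the main analysis assumes that use continues at the pre-event amount. Then: "The secondary analysis will apply censoring rule #2 with the same assumptions as described above".
- **Days (SAP 6.11.1).** "Whether any background TCS is used or not used for each patient is also collected on the diary device", daily from the first dose. The main analysis treats every day after rescue or stopping study drug as a day of use, and missing diary days likewise. The rule #2 sentence for days is narrower than the one for grams: it carries over only the assumptions for missing values.
- **Rescue (Protocol 7.7.4).** "Patients rescued with high- or ultra-high-potency TCS will continue to take investigational product". With systemic rescue, by contrast, "investigational product will be required to be permanently discontinued for the remainder of the 16-week study duration".
- **Rescue tubes (Protocol 7.7.2).** The sponsor does not supply rescue TCS, and "The weights of returned tubes of the high- and ultra-high-potency TCS are not required".

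**The concern.** For IGA or EASI, keeping observed data after topical rescue gives a sensible supplementary analysis. For TCS-free days it is less straightforward, because the rescue is itself a stronger TCS. A patient who swaps moderate-potency background TCS for an ultra-high-potency product can be recorded as not using background TCS. Under rule #2 those days then add to the TCS-free total. The main analysis scores the same days as TCS used.

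At stake is the supportive value of the rule #2 analysis, which is the only check that SAP 6.11.1 offers on how rescue is handled for this endpoint. If the arms differ in topical rescue, part of the difference in TCS-free days reflects which steroid was applied rather than less steroid use.

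**Working it through.** The documents give no size, power or expected value for the TCS endpoints, so there is no plan figure to reproduce on this point. The check traces how a diary day is scored and then sizes the possible shift.

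**Step 1. Who is affected.** Topical rescue leaves the patient on study drug (Protocol 7.7.4), so rule #2 does not censor. Systemic rescue stops study drug permanently, so both rules censor and these patients are outside the problem from then on.

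**Step 2. How one post-rescue day is scored for a patient still on study drug.**

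| Diary entry for background TCS | Main analysis (rule #1) | Secondary analysis (rule #2) |
|---|---|---|
| Used | TCS used | TCS used |
| Missing | TCS used | TCS used |
| Not used | TCS used | TCS-free, even on a day with rescue TCS |

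Only the last row differs. Nothing in SAP 6.11.1 or Protocol 7.7.2 and 7.7.4 changes the rule #2 entry when rescue TCS was applied that day.

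**Step 3. Size for days.** Let rP and rB be the shares with topical rescue while on study drug (placebo, baricitinib), D the days on rescue TCS per rescued patient, and q the share of those days with background TCS recorded as not used. The shift in the mean difference (baricitinib minus placebo) is

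shift = −(rP − rB) × D × q.

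Inputs: Protocol 7.7.4 allows up to 14 consecutive days per course, so D = 14 for one course; the treatment period is 16 × 7 = 112 days, and 14/112 = 12.5% of a rescued patient's days. The rescue shares and q are assumptions, because the documents give neither.

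| Assumed rescue, placebo vs baricitinib | q = 0.25 | q = 1 (full replacement) |
|---|---|---|
| 20% vs 10% | −0.10 × 14 × 0.25 = −0.35 days | −0.10 × 14 × 1 = −1.4 days |
| 30% vs 10% | −0.20 × 14 × 0.25 = −0.7 days | −0.20 × 14 × 1 = −2.8 days |
| 10% vs 10% | 0 | 0 |
| 10% vs 20% | +0.35 days | +1.4 days |

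Against 112 days, 1.4 is 1.25% and 2.8 is 2.5%. The formula is linear in D, so a second course would double each entry. The protocol limits consecutive days but gives no number of courses.

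**Step 4. Grams.** The rule #2 sentence for grams is not limited to missing values, so it has two readings. Taken literally, it includes carrying the pre-rescue amount forward after rescue; there are then no zero grams, but rule #2 handles rescue exactly as rule #1 does and adds no check on it. Alternatively, weighed background tubes count as observed after topical rescue, and the rescue product adds nothing to the total. No usage rate is given, so a shift in grams cannot be computed.

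**The case against.** The strongest reply is that the endpoint is background TCS by definition, so a day with rescue TCS and no background TCS is classified correctly, and rule #2 is meant to use observed data. As a matter of definition that stands. But the SAP's own main analysis does not treat post-rescue days as sparing, and the result will naturally be read as TCS sparing.

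A second reply is that replacement is assumed. Protocol 7.7.4 describes rescue as additional therapy. On clearing, it recommends stopping moderate-potency TCS along with the stronger products and then using low-potency TCS for a further week, which suggests that background TCS may continue during rescue. The diary asks about any use, so one application scores the day as used. This stands, and it is why q runs from a quarter to 1 rather than being fixed at 1.

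A reader might go further than the documents allow in four ways:

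- **That the analysis is biased against baricitinib.** This needs more topical rescue on placebo. It is plausible if the drug works, since rescue is for worsening symptoms, but no rates by arm are given.
- **That rescue days contribute 0 g.** The grams sentence is ambiguous and can be read as imputing pre-rescue use.
- **That the worst-controlled patients look steroid-sparing.** Patients whom topical rescue fails may go on to systemic rescue, and they are then censored under rule #2 too.
- **That a disagreement between the two analyses could not be interpreted.** For days, they differ only in on-drug time after rescue, and SAP 6.10 summarises rescue separately, so a disagreement can be traced to rescue handling.

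**Conclusion.** The point holds for the rule #2 analysis of days without background TCS: a rescue-TCS day with background TCS recorded as not used counts as TCS-free, while the main analysis counts it as a TCS day. The direction is conditional: against baricitinib if topical rescue is more frequent on placebo, neutral if equal, in its favour if reversed. For one 14-day course the illustrative shift is 0.35 to 1.4 of 112 days at 20% versus 10% rescued, and 0.7 to 2.8 days at 30% versus 10%. These figures rest on assumed rescue shares and on how far rescue TCS replaces background TCS.

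For grams the documents support only a finding of ambiguity. The main analyses are unaffected and the endpoints are not multiplicity-adjusted, so this is a low-cost improvement and no threat to the trial's conclusions.

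**What to change.** In SAP 6.11.1, for the rule #2 analysis of days, score every day within a topical rescue episode documented in the eCRF as a day with TCS use. Days after the episode ends stay as observed, so the analysis still differs from the main one. This removes the shift shown above.

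For grams, state whether amounts after topical rescue are observed or set to the pre-rescue amount. If the latter, acknowledge that rule #2 then handles rescue as rule #1 does. A day-level correction for grams is not feasible, because tubes are weighed only at visits up to four weeks apart.

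In the same edit, tie #1 and #2 to the primary and secondary rules of SAP 6.4, and correct the reference in 6.11.1 to rescue medication tubes, since weights of rescue tubes are not required.

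The cost is SAP wording and a merge of rescue records; Protocol 7.7.4 already requires topical rescue to be documented in the eCRF. SAP 6.10 names the rescue therapy page but not its date fields, so a convention for partial or missing rescue dates is needed. No treatment rule and no confirmatory test changes.

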## 6.12. Efficacy Analyses

The general methods used to summarize efficacy data, including the definition of baseline value for assessments are described in Section 6.2. The censoring rules applied to data as well as imputation methods are described in Section 6.4.

Table JAIY.6.4 provides the descriptions and derivations of the primary, secondary, and exploratory efficacy outcomes.

Table JAIY.6.5 provides the detailed analyses including analysis type, method and imputation, population, time point, and comparisons for efficacy analyses.

**Table JAIY.6.4. Description and Derivation of Primary, Secondary and Exploratory Efficacy Outcomes**

Measure	Description	Variable	Derivation / Comment	Imputation Approach if Missing Components
Validated Investigator’s Global Assessment for AD (IGA)	The validated Investigator’s global assessment of the patient’s overall severity of their AD, based on a static, numeric 5-point scale from 0 (clear) to 4 (severe). The score is based on an overall assessment of the degree of erythema, papulation/induration, oozing/crusting, and lichenification.	IGA score	Single item. Range: 0 to 4 0 represents “clear” 4 represents “severe”	Single item, missing if missing.
		Change from baseline in IGA score	Change from baseline: observed IGA score – baseline IGA score	Missing if baseline or observed value is missing.
		
 
▪ IGA [0,1] with <math>\geq 2</math>-point improvement
 
▪ IGA [0]
 
	
 
▪ Observed score of 0 or 1 and change from baseline <math>\leq 2</math>
 
▪ Observed score of 0
 
	
 
▪ Missing if baseline or observed value is missing.
 
▪ Single item, missing if missing.
 

Eczema Area and Severity Index (EASI)	The EASI assesses objective physician estimates of 2 dimensions of atopic dermatitis – disease extent and clinical signs (Hanifin et al 2001) – by scoring the extent of disease (percentage of skin affected: 0 = 0%; 1 = 1-9%; 2 = 10-29%; 3 = 30-49%; 4 = 50-69%; 5 = 70-89%; 6 = 90-100%) and the severity of 4 clinical signs (erythema, edema/papulation, excoriation, and lichenification) each on a scale of 0 to 3 (0 = none, absent; 1 = mild; 2 = moderate; 3 = severe) at 4 body sites (head and neck, trunk, upper limbs, and lower limbs). Half scores are allowed between severities 1, 2 and 3. Each body site will have a score that ranges from 0 to 72, and the final EASI score will be obtained by weight-averaging these 4 scores. Hence, the final EASI score will range from 0 to 72 for each time point.	EASI score	Derive EASI region score for each of head and neck, trunk, upper limbs, and lower limbs as follows: $EASI_{region} = (\text{Erythema} + \text{edema/papulation} + \text{Excoriation} + \text{Lichenification}) * (\text{value from percentage involvement})$ , where erythema, edema/papulation, excoriation, and lichenification are evaluated on a scale of 0 to 3 and value from percentage involvement is on a scale of 0 to 6.  Then total EASI score is as follows: $EASI = 0.1 * EASI_{\text{head and neck}} + 0.3 * EASI_{\text{trunk}} + 0.2 * EASI_{\text{upper limbs}} + 0.4 * EASI_{\text{lower limbs}}$	N/A – partial assessments cannot be saved.
		
 
▪ Change from baseline in EASI score
 
▪ Percent change from baseline EASI score
 
	Change from baseline: observed EASI score – baseline EASI score % change from baseline: $100 \times \frac{\text{Observed score} - \text{Baseline}}{\text{Baseline}}$	Missing if baseline or observed value is missing.
		EASI50	% Improvement in EASI score from baseline $\geq 50\%$ : % change from baseline $\leq -50$	Missing if baseline or observed value is missing.
		EASI75	% Improvement in EASI score from baseline $\geq 75\%$ : % change from baseline $\leq -75$	Missing if baseline or observed value is missing.
		EASI90	% Improvement in EASI score from baseline $\geq 90\%$ : % change from baseline $\leq -90$	Missing if baseline or observed value is missing.
Body Surface Area (BSA) Affected by AD	Body surface area affected by AD will be assessed for 4 separate body regions and is collected as part of the EASI assessment: head and neck (including genital region), upper extremities, and lower extremities	BSA score	Use the percentage of skin affected for each region (0 to 100%) in EASI as follows:  $BSA \text{ Total} = 0.1 * BSA_{\text{head and neck}} + 0.3 * BSA_{\text{trunk}} + 0.2 * BSA_{\text{upper limbs}} +$	N/A – partial assessments cannot be saved.

	(including the buttocks). Each body region will be assessed for disease extent ranging from 0% to 100% involvement. The overall total percentage will be reported based off of all 4 body regions combined, after applying specific multipliers to the different body regions to account for the percent of the total BSA represented by each of the 4 regions.		$0.4 * BSA_{lower\ limbs}$	
		Change from baseline in BSA score	Change from baseline: observed BSA score – baseline BSA score	Missing if baseline or observed value is missing.
SCORing Atopic Dermatitis (SCORAD)	The SCORing Atopic Dermatitis (SCORAD) index uses the rule of nines to assess disease extent (head and neck 9%; upper limbs 9% each; lower limbs 18% each; anterior trunk 18%; back 18%; and genitals 1%). It evaluates 6 clinical characteristics to determine disease severity: (1) erythema, (2) edema/papulation, (3) oozing/crusts, (4) excoriation, (5) lichenification, and (6) dryness on a scale of 0 to 3 (0=absence, 1=mild, 2=moderate, 3=severe). The SCORAD index also assesses subjective symptoms of pruritus and sleep loss in the last 72 hours on visual analogue scales (VAS) of 0 to 10 where 0 is no itch or sleep loss and 10 is worst imaginable itch or sleep loss. These 3 aspects: extent of disease, disease severity, and subjective symptoms combine to give a maximum possible score of 103 (Stalder et al. 1993; Kunz et al. 1997; Schram et al. 2012).	SCORAD score	SCORAD = A/5 + 7B/2 + C, where A is extent of disease, range 0-100 B is disease severity, range 0-18 C is subjective symptoms, range 0-20	Missing if components A and B are missing or if component C is missing. Partial assessments performed by physician cannot be saved and partial assessments performed by subject cannot be saved.
		
 
▪ Change from baseline in SCORAD score
 
▪ Percent change from baseline in SCORAD score
 
	Change from baseline: observed SCORAD score – baseline SCORAD score  % change from baseline: $100 \times \frac{Observed\ score - Baseline}{Baseline}$	Missing if baseline or observed value is missing.
		SCORAD75	% Improvement in SCORAD from baseline $\geq 75\%$ : % change from baseline $\leq -75$	Missing if baseline or observed value is missing.
		SCORAD90	% Improvement in SCORAD from baseline $\geq 90\%$ : % change from baseline $\leq -90$	Missing if baseline or observed value is missing.

Table JAIY.6.5. Description of Primary, Secondary and Exploratory Efficacy Analyses

Measure	Variable	Analysis Method (Section 6.2.3)	Population (Section 6.2.1)	Comparison/Time Point	Analysis Type
Validated Investigator's Global Assessment for AD (IGA)	Proportion of patients achieving IGA [0,1] with a $\geq 2$ -point improvement	Logistic regression using NRI	ITT	Bari 4 mg or Bari 2 mg vs PBO; Week 16	Primary analysis
			PPS	Bari 4 mg or Bari 2 mg vs PBO; Week 16	Sensitivity analysis
			ITT	Bari 4 mg or Bari 2 mg vs PBO; Week 4	Secondary analysis
		Logistic regression using pMI and Tipping Point	ITT	Bari 4 mg or Bari 2 mg vs PBO; Week 16	Sensitivity analysis
	Proportion of patients achieving IGA [0]	Logistic regression using NRI	ITT	Bari 4 mg or Bari 2 mg vs PBO; Week 16	Secondary analysis
Eczema Area and Severity Index (EASI)	
 
EASI score
 
Change from baseline in EASI score
 
Percent change from baseline in EASI score
 
	MMRM	ITT	Bari 4 mg or Bari 2 mg vs PBO; Week 16	Key secondary analysis
			PPS	Bari 4 mg or Bari 2 mg vs PBO; Week 16	Sensitivity analysis
		ANCOVA using mLOCF	ITT	Bari 4 mg or Bari 2 mg vs PBO; Week 16	Sensitivity analysis
		pMI and Tipping Point	ITT	Bari 4 mg or Bari 2 mg vs PBO; Week 16	Sensitivity analysis
	
 
Proportion of patients achieving EASI50
 
	Logistic regression using NRI	ITT	Bari 4 mg or Bari 2 mg vs PBO; Week 16	Secondary analysis
	
 
Proportion of patients achieving EASI75
 
Proportion of patients achieving EASI90
 
	Logistic regression using NRI	ITT	Bari 4 mg or Bari 2 mg vs PBO; Week 16	Key secondary analysis
			PPS	Bari 4 mg or Bari 2 mg vs PBO; Week 16	Sensitivity analysis
		pMI and Tipping Point	ITT	Bari 4 mg or Bari 2 mg vs PBO; Week 16	Sensitivity analysis
Body Surface Area (BSA) Affected by AD	
 
BSA score
 
Change from baseline in BSA score
 
	MMRM	ITT	Bari 4 mg or Bari 2 mg vs PBO; Week 16	Secondary analysis
		ANCOVA using mLOCF	ITT	Bari 4 mg or Bari 2 mg vs PBO; Week 16	Sensitivity analysis

Measure	Variable	Analysis Method (Section 6.2.3)	Population (Section 6.2.1)	Comparison/Time Point	Analysis Type
SCORing Atopic Dermatitis (SCORAD)	
 
• SCORAD score
 
• Change from baseline in SCORAD score
 
• Percent change from baseline in SCORAD score
 
	MMRM	ITT	Bari 4 mg or Bari 2 mg vs PBO; Week 16	Secondary analysis
		ANCOVA using mLOCF	ITT	Bari 4 mg or Bari 2 mg vs PBO; Week 16	Sensitivity analysis
	Proportion of patients achieving SCORAD75	Logistic regression using NRI	ITT	Bari 4 mg or Bari 2 mg vs PBO; Week 16	Key secondary analysis
			PPS	Bari 4 mg or Bari 2 mg vs PBO; Week 16	Sensitivity analysis
		Logistic regression using pMI	ITT	Bari 4 mg or Bari 2 mg vs PBO; Week 16	Sensitivity analysis
	Proportion of patients achieving SCORAD90	Logistic regression using NRI	ITT	Bari 4 mg or Bari 2 mg vs PBO; Week 16	Secondary analysis
		pMI and Tipping Point	ITT	Bari 4 mg or Bari 2 mg vs PBO; Week 16	Sensitivity analysis
Skin Infections	Proportion of patients developing skin infections requiring antibiotic treatment	Fisher's exact	ITT	Bari 4 mg or Bari 2 mg vs PBO; Week 16	Secondary analysis

Abbreviations: ANCOVA = analysis of covariance; Bari = baricitinib; ITT = intent-to-treat; mLOCF = modified last observation carried forward;

MMRM = mixed model repeated measures; NRI = nonresponder imputation; PBO = placebo; pMI=placebo multiple imputation; PPS = per protocol set.

Notes: (1) for all other post-baseline visits not mentioned in the table, but collected for the measures as specified in the protocol, the analyses will be made as exploratory analyses.

(2) All primary and key secondary analyses will be performed for Japan population. Other key secondary and exploratory analysis may be performed for Japan population.

